C) This would be a randomized, double-blind, placebo controlled trial. 1/2 of the patients would receive intra-operative secretin, the other half would receive saline placebo. Both the surgeon and patient would be blinded to the randomization assignment. The advantage of giving secretin would be that it may allow for the identification of a leak intra-operatively and subsequently allow for repair if the leak was identified prior to abdominal wall closure. While the safety profile of the drug is excellent, receiving the medication could theoretically cause an increased intraductal pressure which may cause a leak when one was not already present.

D) Human subjects are needed to evaluate intra-operative, intravenous secretin in patients undergoing pancreatic duct resection.

4. Design, procedures, materials and methods:

Use a level of detail similar to what would be used when submitting an article for publication in a peer reviewed journal. Explain the study procedures, data collection, and analysis process. Please define terms and explain concepts which might be confusing to reviewers who are not expert in the area of the study. If a formal protocol for the study exists, page references to the protocol are acceptable.

This study design is a prospective, double-blind, randomized-controlled trial. We will enroll patients in our institution undergoing pancreatic resection to receive either 1) one dose weight-based Secretin to be given once the closure of the pancreatic resection margin is complete 2) saline placebo.

Consent and basic demographics will be garnered by the physician in an office visit once the surgery has been scheduled and consent for the surgery is being obtained. The consent will be validated by the treating surgeon in the pre-procedure area on the day of the surgery.

The patient will undergo the scheduled surgery. Once the pancreatic anastomosis has been deemed acceptable by the attending physician, but prior to abdominal closure, the patient will be randomized to receive either Secretin (0.2 mcg/kg) or saline placebo. The attending surgeon will be blinded to this assignment.

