CRF, and then building a multivariable logistic regression model using the categorical variable of drain amylase >3x the upper limit of normal. The data from the multivariate regression will be reported as Odds Ratios.

The secondary outcomes are both categorical and continuous variables and thus we will use the Fisher's Exact test as well as the two-tailed student's t-test. A multivariable analysis is not planned for evaluating the secondary variable.

Randomization will occur in a block format of 5 and will be generated by the primary investigators.

c) Justify the sample size, using the concepts of power, type I error, and effect size if applicable. If a formal protocol for the study exists, page references to the protocol are acceptable.

A clinically significant absolute decrease of 15% (20% to 5%) in the pancreatic duct leak rate. Based on these estimates and a two-tailed test comparing proportions using the statistical calculator (<http://homepage.stat.uiowa.edu/~rlenth/Power>), we project an estimated sample size of **176 participants (88 per arm)** to demonstrate an absolute 15% reduction in the leak rate with 80% power at a two-sided alpha level of 0.05.

8. Data and Safety Monitoring:

Describe plans for data and safety monitoring to ensure the safety of subjects and the quality of the data. As described in federal guidance "... a variety of types of monitoring may be anticipated depending on the nature, size, and complexity of the trial. In many cases, the principal investigator would be expected to perform the monitoring function." This plan should include monitoring to determine:

The progress of the trial, including periodic assessments of data quality and timeliness, participant recruitment, accrual and retention, participant risk versus benefit, and other factors that can affect study outcome. Monitoring should also consider factors external to the study when interpreting the data, such as scientific or therapeutic developments that may have an impact on the safety of the participants or the ethics of the study.

Note: This section does not request information related to sponsor study monitor visits. This section requires a description of an adequate data and safety monitoring plan.

Interim analysis will be performed once 50% (88) patients have been enrolled. If more than 66% of cases of duct leak are in a particular study group, a formal comparison between groups will be performed with the use of a two-sided stopping boundary of 0.005%.

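### The interim rule compares the arms only if more than 66% of leak cases fall in one arm; it ignores denominators, while blocks of 5 do not guarantee the stated 1:1 allocation.

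*Combined protocol and SAP*

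**What the plan says.** Section 8 (Data and Safety Monitoring) sets one look: "Interim analysis will be performed once 50% (88) patients have been enrolled". What happens then depends on a share of cases: "If more than 66% of cases of duct leak are in a particular study group", the arms are formally compared; otherwise no comparison is specified. The boundary for that comparison is "use of a two-sided stopping boundary of 0.005", followed in the text by a percent sign. DSMB co-heads who take no part in the trial are named, but no other between-arm rule is given.

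On allocation, Section 3C assigns half the patients to each arm and Section 7c gives 88 per arm. Section 7b states "Randomization will occur in a block format of 5" and does not give the split within a block.

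On harm, Section 3C recognises that "receiving the medication could theoretically cause an increased intraductal pressure which may cause a leak when one was not already present". Section 4 provides drain amylase on POD 1 to 5 and 30 days of follow-up for leak and its sequelae, with a causality rating but no comparison between arms.

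**The concern.** The plan names a harm specific to this setting, a leak provoked by the drug, and the one numerical rule that could show it is a raw share of cases. A share measures relative risk only if the arms are the same size. An odd block cannot be balanced, so the allocation rule does not secure what the gate relies on. With equal arms, a true doubling of the leak rate gives an expected share of two thirds, almost exactly at the cut-off, so whether any comparison is made is close to a coin toss. If the gate stays shut, the text does not require anyone to look at leak rates by arm. The look is also triggered by enrolment, so some outcomes will be incomplete.

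**Working it through.** **The plan's own figure.** Section 7c assumes "A clinically significant absolute decrease of 15% (20% to 5%) in the pancreatic duct leak rate" "with 80% power at a two-sided alpha level of 0.05". With the mean rate 0.125:

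n = [1.96·√(2·0.125·0.875) + 0.842·√(0.20·0.80 + 0.05·0.95)]² / 0.15² = 75.1, so 76 per arm.

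With continuity correction: (75.1/4)·[1 + √(1 + 4/(75.1·0.15))]² = 87.9, so 88 per arm. The plan's 176 is reproduced. The plan states no operating characteristics for the gate.

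**Where the gate sits.** With arm sizes n_S and n_P and leak rates p_S and p_P, the expected secretin share is about n_S·p_S / (n_S·p_S + n_P·p_P). At equal arms it reaches 0.66 when the rate ratio is 0.66/0.34 = 1.94. For 40% v 20%:

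- 44 v 44: 17.6/(17.6 + 8.8) = 0.667
- 40 v 48: 16/(16 + 9.6) = 0.625
- 48 v 40: 19.2/(19.2 + 8) = 0.706
- 35 v 53: 14/(14 + 10.6) = 0.569

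**How often it opens toward secretin.** Exact enumeration of two independent binomials, summing the probability of every outcome with secretin leaks / all leaks > 0.66. The 20% is the plan's control rate. The 30% and 40% are my assumptions.

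| Secretin v placebo (n) | 20% v 20% | 30% v 20% | 40% v 20% |
|---|---|---|---|
| 44 v 44 | 7.7% (15.4% either way) | 26.6% | 54.1% |
| 40 v 48 | | | 34.3% |
| 48 v 40 | | | 73.2% |
| 35 v 53 | 1.1% | 5.2% | 15.1% |
| 53 v 35 | 30.7% | 66.7% | 90.1% |

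Doublings from lower rates at 44 v 44 (5 to 10%, 10 to 20%, 15 to 30%) are missed in 42.5% to 45.4% of trials, so the result hardly depends on the base rate.

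**What blocks of 5 produce.** 176/5 = 35.2, so the list does not end on a complete block. If each block is randomly 3:2 or 2:3 (an assumption), simulation gives a secretin arm at 88 patients with mean 44, SD 2.2 and 95% range 40 to 48, and exactly 44 in 18% of sequences. Averaged over those sequences, the gate opens toward secretin in 53.9% of doublings, almost as at 44 v 44. A given trial, however, has one allocation, and over that range the figure runs from 34% to 73%. The 53 v 35 rows need every block to lean the same way (88·0.6 = 52.8).

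**Does the gate change formal stopping?** The interim test is not named, so I used the two-sided Fisher test that Section 7b names for the primary endpoint. Chance of crossing in the harm direction, 40% v 20%:

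| Secretin v placebo (n) | Boundary | With gate | Without gate |
|---|---|---|---|
| 44 v 44 | 0.005% | 1.2% | 1.2% |
| 44 v 44 | 0.005 | 15.8% | 15.8% |
| 35 v 53 | 0.005% | 1.4% | 1.4% |
| 35 v 53 | 0.005 | 12.5% | 18.3% |

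At 40 v 48 and 0.005, the same enumeration gives 19.3% with the gate and 19.7% without. As a DSMB signal at nominal p ≤ 0.05, which is not a stopping rule, 40 v 48 gives 33.6% with the gate and 49.3% without.

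Example: 17/40 v 9/48 leaks is 42.5% v 18.8%, Fisher p = 0.019. The share is 17/26 = 65.4%, so no comparison would be made.

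**Follow-up at the look.** Section 13b implies 120·0.80 = 96 patients a year, or 8 a month. About 8 of the 88 would lack complete 30-day data. Over 5 days, 96·5/365 = 1.3, so one or two would lack POD 5 amylase.

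**The case against.** The strongest reply is that the gate is not what limits stopping. At 44 v 44, every doubled-leak result with a realistic chance of crossing either version of the boundary already has a share above 66%. Even at nominal 0.05 the gate costs only 1.4 points (44.8% to 43.4%). This stands. A reader might infer from the 46% miss rate that the gate hides harm that would otherwise have stopped the trial; at equal arms that is not so, and the boundary is the binding limit.

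A reader might also infer that blocks of 5 cannot give equal arms. One block cannot, but a mixture of 3:2 and 2:3 blocks averages 1:1 and can reach 44 v 44. The text supports only that equality is not guaranteed. The 53 v 35 case contradicts the stated half-and-half allocation, so it is a worst case allowed by an unstated split, not an expectation.

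Third, the gate is not the only safeguard. There is a DSMB and a 30-day follow-up for leak, infection, hemorrhage, drain placement and reoperation. That stands too, but neither has a between-arm rule attached.

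Fourth, opening the gate with no effect present does little damage, because it only triggers a test. At 53 v 35 the chance of then crossing toward the larger arm is about 0.1% at 0.005.

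Finally, the primary outcome rests on drain amylase, measured up to POD 5, so the 30-day lag mainly affects late leaks and sequelae. The leak definition in Section 4 does also require a related clinical development, so the lag is not irrelevant.

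**Conclusion.** The point holds in a limited form and should be corrected. The only pre-specified quantitative between-arm interim rule uses a case share with no denominators, and the block size does not secure the equal arms that a share needs. For one and the same doubling, the chance that any comparison toward harm is made varies about twofold (34% to 73%) over the arm sizes that random 3:2 and 2:3 blocks would ordinarily give.

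The effect on formal stopping is nil at equal arms, 0.4 points at 40 v 48 with a 0.005 boundary, and about 6 points at 35 v 53 with that boundary. At 0.005% as written, it is nil at both 44 v 44 and 35 v 53. The larger consequence is for information: with the gate shut, the plan does not commit to showing the DSMB leak rates by arm.

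This rests on a 20% placebo rate, an assumed rise to 40%, a Fisher test at the look, and an assumed block split. The documents do not show that the gate masks a harm the boundary would have caught under the intended 1:1 allocation.

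**What to change.** - **Section 7b:** replace blocks of 5 with even blocks, for example randomly mixed 4 and 6, each split 1:1. The arms then never differ by more than 3 patients at any point. Blocks of 4 alone would fit 176 exactly (44 blocks) but are easier to predict.
- **Section 8, gate:** drop the 66% condition. At the look, always give the DSMB leak counts, denominators and rates by arm, and base the formal comparison on rates. Name the test.
- **Section 8, boundary:** state whether 0.005% or 0.005 is intended, since the crossing probabilities differ by more than a factor of ten. Removing the gate does not settle this.
- **Section 8, data cut:** trigger the look when 88 dosed patients have completed outcome follow-up, not at enrolment of the 88th.

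The cost is wording in two sections, a new randomization list, and a look up to about one month later, with about 8 more patients enrolled meanwhile. The sample size is unchanged.

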a) *List tests, visits, and procedures performed for only research purposes. These services are outside the standard of care. They would not be performed if the individual were not a research participant, and may not be billed to a health insurance plan.*

Note: 6a information must also be in "How is this different . . ." section of the consent form.

The administration of Secretin or placebo is for research purposes only and will not be billed to the patient. Drain placement, drain amylase measurement and the two week follow-up visit are per standard of care and will be billed directly to the patient.

b) *List the tests, visits, and procedures that may be standard care, but for which the funding agency for the study is paying.*

None

c) *Will the funding agency for the study be responsible for the above costs? Yes No
If No, describe who will be responsible (i.e., department or participant).*

Secretin will be supplied by ChiRhoClin, Inc and saline placebo will be supplied by the Section of Gastroenterology and Hepatology out of research funds maintained by the primary investigators. No additional tests, visits, or procedures will be performed for research purposes only.

PLEASE ENCLOSE THE DHMC BILLING GRID/PLAN. Also enclose the schedule of events or table listing all procedures from the sponsor protocol.

7. Statistical Methods and Review Statement:

a) *Specify the primary endpoint, as well as other endpoint(s).*

Primary Objective:

1. Pancreatic leak as defined by the ISGPF definition of post-operative pancreatic leaks

Secondary Objective:

1. Assess whether intervention is performed intra-operatively on the pancreatic anastomosis following Secretin or placebo injection.
2. Assess degree to which leakage severity, as a complication, increases length of stay.

b) *State the statistical analysis plan, including all hypothesis tests (e.g., t-test, chi-square), and estimation methods related to the primary endpoint. If a formal protocol for the study exists, page references to the protocol are acceptable.*

For the analysis of the primary endpoint, a categorical variable, we will use a two-tailed Fisher's Exact test to determine a p-value. We will then be able to calculate an absolute and relative risk reduction. We will also evaluate this variable using a student's t-test for means of amylase levels in the drain fluid. We will plan on performing univariate analysis of all of the potentially contributing variables outlined in the

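### The interim stopping boundary is written as 0.005% (two-sided p of 0.00005), which at about 44 per arm is almost never crossed; the intended value needs confirming and restating as a p-value

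*Combined protocol and SAP*

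**What the plan says.** Section 8 (Data and Safety Monitoring) sets the timing: "Interim analysis will be performed once 50% (88) patients have been enrolled". A formal test follows only on a condition: "If more than 66% of cases of duct leak are in a particular study group". In that event "a formal comparison between groups will be performed with the use of a two-sided stopping boundary of 0.005", with a percent sign immediately after the number.

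The boundary is not expressed as a p-value or z-value anywhere. No boundary method or alpha-spending rule is named, and the test to be used at the interim is not specified. Section 7c gives the only other significance level, as a decimal: "with 80% power at a two-sided alpha level of 0.05". Section 7b names the primary test: "we will use a two-tailed Fisher's Exact test to determine a p-value".

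**The concern.** A two-sided interim level of 0.00005 is extremely strict for a look at 88 patients with a binary outcome and few expected events. The other significance level in the protocol carries no percent sign, so this one may be a slip for 0.005. That value is close to a two-look O'Brien-Fleming interim level (|z| about 2.80, p about 0.005). The resemblance makes a slip plausible but does not prove it.

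Two things are at stake. Applied literally, the rule would hardly ever operate, for benefit or for harm. Harm is not an idle direction here, because section 3C says that "receiving the medication could theoretically cause an increased intraductal pressure which may cause a leak when one was not already present". Also, a DSMB left to decide what the percent sign means might have to do so after seeing unblinded data on which the two readings disagree.

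**Working it through.** **Inputs.** Interim at 88 patients (section 8), taken as 44 per arm under 1:1 allocation (section 3C). Leak rates 20% v 5% (section 7c). Fisher's exact test (section 7b), assumed to apply at the interim too. Outcomes assumed known for all 88. The documents give no harm rate, so secretin leak rates of 40%, 50% and 60% are assumptions shown as a range.

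**The plan's own figure.** With p1 = 0.20, p2 = 0.05 and mean 0.125:

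n = [1.960·√(2·0.125·0.875) + 0.8416·√(0.16 + 0.0475)]² / 0.15² = (0.9167 + 0.3834)² / 0.0225 = 75.1, so 76 per arm.

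With the continuity correction, (75.1/4)·[1 + √(1 + 4/(75.1·0.15))]² = 87.9, so 88 per arm. This matches the stated 176 in total.

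**Converting the boundary.** 0.005% = 0.005/100 = 0.00005, or |z| = 4.06. For comparison, 0.005 is |z| = 2.81.

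**Which splits cross 0.00005.** For 0 v k leaks with 44 per arm, the two-sided Fisher p is 2·C(44,k)/C(88,k):

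- 0 v 9: 0.0025
- 0 v 11: 0.00048
- 0 v 13: 0.000086 (does not cross)
- 0 v 14: 0.000036 (crosses)

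The smallest p available with 13 or fewer leaks in total is 0.000086, so at least 14 leaks are needed. Other minimal crossing splits are 1 v 17, 2 v 19 and 9 v 29.

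The design effect predicts 44·0.05 = 2.2 and 44·0.20 = 8.8 leaks, about 2 v 9, for which p = 0.049. The chance of 13 or fewer leaks at the design effect is 80%. If leaks double, 44·0.40 = 17.6 are expected on secretin against 8.8 on placebo, where 29 would be needed to cross.

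**Chance of crossing.** Sum b(x; 44, 0.20)·b(y; 44, π) over all tables with Fisher p at or below the boundary, where b is the binomial probability and π is the secretin leak rate:

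| Secretin rate (placebo 20%) | p ≤ 0.00005 | p ≤ 0.005 |
|---|---|---|
| 0% | 4.4% | 53.0% |
| 5% (design) | 0.55% | 14.6% |
| 40% (assumed) | 1.2% | 15.8% |
| 50% (assumed) | 9.1% | 48.6% |
| 60% (assumed) | 35% | 82.8% |

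The difference between the columns is the chance that the two readings give opposite decisions. From unrounded values it is 14.0% at the design effect, 14.6% at 40% and 39.5% at 50%.

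**Is the 66% trigger responsible?** No. It is met 89% of the time at the design effect, and applying it leaves every figure in the table unchanged to one decimal place.

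**Sensitivity at 0.00005.** Blocks of 5 cannot balance 1:1. Seventeen 3:2 blocks in one direction plus a partial block of three give 17·3 + 3 = 54 v 34. Over splits from 34/54 to 54/34, crossing ranges from 0.13% to 1.8% at the design effect and from 1.1% to 1.7% on doubling. A pooled z-test at 44/44 gives 0.57% and 1.6%.

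**Overall error and power.** Tables that continue were convolved with a second 44/44, with the final Fisher test at 0.05. At a common 20% leak rate, exact type I error is 3.19% with 0.00005 and 3.27% with 0.005. Power at 20% v 5% is 83.8% for both. With 0.005 and a final 0.05, type I error runs from 1.82% at a 5% common rate to about 4.2% at 50%, the maximum over that range. A normal approximation, which ignores the conservatism of Fisher's test, gives 5.19%, or 4.99% with a final alpha of 0.048.

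**The case against.** The strongest reply is that nothing has been miscalculated. A boundary of 0.00005 is legitimate, if severe, and reluctance to stop early for benefit is defensible in a study the abstract calls a pilot. Even at 0.005 the trial would continue 85% of the time at the design effect, and the final inference is practically the same under either reading. The harm rates are hypothetical: the protocol offers only a theoretical mechanism and describes secretin's risks as modest. Moreover 0.005 would itself miss a doubling of leaks 84% of the time, so clarifying the value does not create a harm monitor. Finally, the look is triggered by enrolment, and patients given no study drug are not followed, so fewer than 44 per arm may have outcomes.

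Much of this stands. The literal value is not proved wrong, type I error is not inflated, and the harm figures depend on assumed rates. The literal rule does gain some chance of operating if harm is extreme (50% to 60%). But a deliberate choice this strict would need a stated basis, and none is given. Fewer patients with outcomes would make the boundary harder still to cross. None of these replies removes the ambiguity, which changes decisions on data that could well arise.

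**Conclusion.** The point holds. As written, the trial's only numerical stopping rule has under a 1% chance of operating at the design effect, under 5% if every leak on secretin were prevented, and about 1% if leaks doubled. Reading the boundary as 0.005 raises these chances to between about 15% and 53%. The documents do not settle which was meant. The main figures assume equal arms, Fisher's test at the interim, complete outcomes for 88 patients and, for harm, the assumed secretin rates. The conclusion for the design effect and for a doubling survives the unequal splits and the z-test. The final analysis is not threatened; the interim safeguard is, and the wording should be settled before the look takes place.

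**What to change.** The sponsor should confirm the intended boundary, name the method or reasoning behind it, and restate it in section 8 as a two-sided p-value, together with the interim test and the final alpha.

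- **If the percent sign is a slip:** write two-sided p < 0.005. The final Fisher test can stay at 0.05, since exact overall type I error is then 3.3% at a 20% leak rate and at most about 4.2% at common rates from 5% to 50%, with power 83.8%. If a nominal adjustment is preferred, a final alpha of 0.048 gives power of 82.6%. The text should also say that 0.005 is not a sensitive monitor for harm.
- **If 0.00005 is intended:** say so, and report its crossing chances so that the DSMB knows how seldom the rule will act.

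The 66% trigger can stay. The cost is one line of protocol or DSMB wording, no added patients, and no loss of power, or 83.8 − 82.6 = 1.2 points if 0.048 is chosen.

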Synthetic secretin is FDA approved to diagnose exocrine pancreas dysfunction by the functional secretin stimulated pancreas function test and to facilitate pancreatic duct cannulation during ERCP. It is identical in amino acid sequence to native human secretin.

There has not been any reported adverse drug reaction to human secretin stimulation. Rarely, in over 1000 patients who have undergone Secretin-enhanced pancreatic function tests, there is transient vasodilatory effect resulting in flushing of the face and lips with stable vital signs. Therefore, the risks of administering intravenous secretin are modest as described in the package label.

In doses (800cu SQ bid x 7 days) given in clinical studies greater than those offered in the current study, there were no adverse events reported

Secretin is not known to increase the risk of acute pancreatitis episodes in patients with chronic pancreatitis not presently having an acute pancreatitis attack. No allergic reactions have been reported with secretin in commercial use although the administration of a test dose 0.2 mcg IV is still recommended. No significant hemodynamic effects have been observed following administration of secretin. Otherwise, the risks of administering secretin are modest as described in the package label.

The risk of confidentiality should be low given the case report form will be only available to [name] and will be kept in a locked cabinet. All data will be entered on a password-protected Microsoft Excel spreadsheet. Any statistical analysis will be done with patient study numbers and initials for identification of patient.

15. Risk/Benefit analysis:

Describe why the risks to subjects are reasonable in relation to the anticipated benefits to participants and in relation to the importance of the knowledge that may reasonably be expected to result from the study.

A potential risk reduction of up to 15% for pancreatic duct leaks outweighs the given theoretical risks of one time Secretin administration.

16. Research Setting

a) Is this a multi-center study?

Yes No

If yes: Are you the lead investigator? Yes No *If*

you are NOT the lead investigator:

Name of lead investigator:

Institution where the lead investigator is located:

b) List all sites where research will take place and the CPHS at Dartmouth College is the reviewing IRB (e.g. DHMC Alliance Hospitals, DHMC Clinics, WRJ VAMC):

Dartmouth-Hitchcock Medical Center

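### The only written stopping rule asks for the same extreme evidence of harm as of benefit: if secretin doubled the leak rate, it would be crossed about 1% of the time as printed, or 16% if 0.005 was meant

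*Combined protocol and SAP*

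**What the plan says.** Section 8 (Data and Safety Monitoring) sets a single look: "Interim analysis will be performed once 50% (88) patients have been enrolled". A screen follows: "If more than 66% of cases of duct leak are in a particular study group", then "a formal comparison between groups will be performed with the use of a two-sided stopping boundary of 0.005". A percent sign is printed directly after that number, so the literal boundary is p = 0.00005. The section names two DSMB co-heads who take no part in the trial, and gives them no further criterion. The 30-day follow-up and causality scale in Section 4 carry no stopping threshold. The case report form appendix is not among the documents.

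Section 3, part C, gives the relevant risk: "receiving the medication could theoretically cause an increased intraductal pressure which may cause a leak when one was not already present". Section 15 rests the risk-benefit case on this sentence: "A potential risk reduction of up to 15% for pancreatic duct leaks outweighs the given theoretical risks of one time Secretin administration".

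**The concern.** The harm described in Section 3C is the primary outcome moving the wrong way. Because the boundary is two-sided, it is also the only written criterion for stopping if that happens.

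A very strict interim boundary makes sense for benefit, where it protects the type I error of an efficacy claim. That reason does not carry over to harm, because stopping when secretin appears to cause leaks cannot produce a false claim of benefit.

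Section 15 accepts the risk as theoretical, so the one planned look should have a reasonable chance of prompting action if the risk proves real. If it does not, the second half of the trial exposes another 44 patients to secretin.

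**Working it through.** **Inputs**
- Look at 88 patients (Section 8). I assume 44 per arm, all evaluable.
- Leak rates from Section 7c: "A clinically significant absolute decrease of 15% (20% to 5%) in the pancreatic duct leak rate". The placebo rate is therefore 20%. The documents give no harmful secretin rate, so 30% to 60% is an assumed range.
- Test: Section 8 names none for the interim. Section 7b says "For the analysis of the primary endpoint, a categorical variable, we will use a two-tailed" Fisher's exact test, and I use that.
- Boundary: 0.00005 as printed, or 0.005 if the percent sign is a slip.

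**Reproducing the plan's sample size**

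For 20% v 5%, two-sided alpha 0.05 and 80% power, the mean rate is 0.125 and the uncorrected size is

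n = [1.960·√(2·0.125·0.875) + 0.842·√(0.20·0.80 + 0.05·0.95)]² / 0.15² = 75.1, or 76 per arm.

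With the continuity correction, (75.1/4)·[1 + √(1 + 4/(75.1·0.15))]² = 87.9, or 88 per arm. This matches the plan.

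**What the rule needs when placebo has 9 of 44 leaks (20%)**

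| Event | Secretin leaks | Check |
|---|---|---|
| 66% screen opens | 18 | 18/27 = 66.7% |
| One-sided Fisher p ≤ 0.05 | 18 | p = 0.032 |
| Two-sided p < 0.005 | 23 (52% of 44) | p = 0.0036 |
| Two-sided p < 0.00005 | 29 (66% of 44) | p = 0.00003; 28 gives 0.00008 |

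**Probability of crossing against secretin**

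Let s and c be the secretin and placebo leak counts. Sum Bin(s; 44, secretin rate) × Bin(c; 44, placebo rate) over all (s, c) with s/(s + c) > 0.66 and two-sided Fisher p below the boundary. The screen column uses the first condition only. The last column uses one-sided Fisher p ≤ 0.05 with no screen.

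| Secretin v placebo | Screen opens | Crossed, as printed | Crossed, 0.005 | One-sided p ≤ 0.05 |
|---|---|---|---|---|
| 20% v 20% | 7.7% | 0.001% | 0.1% | 2.8% |
| 30% v 20% | 27% | 0.05% | 2.4% | 21% |
| 35% v 20% | 40% | 0.3% | 6.8% | 38% |
| 40% v 20% | 54% | 1.2% | 16% | 57% |
| 50% v 20% | 79% | 9.1% | 49% | 87% |
| 60% v 20% | 93% | 35% | 83% | 98% |
| 5% v 20% (planned benefit) | 0.1% | below 0.001% | below 0.001% | 0.001% |

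**Sensitivity**

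Section 7b says "Randomization will occur in a block format of 5", and blocks of that size cannot split evenly. At 40% v 20%, using chi-square or splits from 40/48 to 48/40 gives 1.2% to 1.8% as printed and 16% to 22% at 0.005. The trial therefore continues under the written rule about 98% to 99% of the time as printed, or 78% to 84% at 0.005. With an assumed 10% placebo rate, a doubling to 20% is caught 0.06% (printed), 3.2% (0.005) and 27% (one-sided 0.05) of the time.

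**What is at stake at 40% v 20%**
- Excess leaks expected among the remaining 44 secretin patients: 44 × (0.40 − 0.20) = 8.8.
- Most that a harm guideline could save, if every trigger stopped the trial at once: 8.8 × (0.569 − 0.158) = 3.6 against the 0.005 reading, and 8.8 × (0.569 − 0.012) = 4.9 against the printed one.
- The final two-sided Fisher test at 88 per arm would show this harm 79% of the time, but only after all 88 secretin patients had been dosed.

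**The case against.** **The 66% screen already flags harm.** At 40% v 20% it opens against secretin 54% of the time, close to the 57% for the proposed guideline, and only 4.7 points of that 57% fall outside the screen. At 30% v 20% the screen opens more often (27% v 21%). This is a fair comparison and limits what the guideline adds in detection. But opening the screen only leads to a test against the same extreme boundary and attaches no other action. With 25 v 9 leaks (p = 0.0009), the printed boundary is still not reached.

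**The DSMB can act on judgement.** It can. A reader might infer that the trial has no protection against harm or must run on below the boundary. The documents do not say that. They give a boundary for stopping and are silent on what follows short of it.

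**The harm is hypothetical and partly mitigated.** This stands. Section 3C calls it theoretical, Section 14 describes the drug's risks as modest, and no document gives a harm rate. Section 4 has the surgeon inspect the pancreas 10 minutes after dosing, so an induced leak might be seen and repaired before closure. The probabilities above are conditional on a net harm that survives that step.

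**Stronger readings that fail.** Leak induction is not the only drug effect named: Section 14 also mentions flushing and raises allergy, with a test dose still recommended. Leak induction is the named harm that would worsen the primary outcome. Continuation at 98% or more applies only to the printed boundary. Nor would the guideline avert all 8.8 excess leaks. It is non-binding, and at 120 × 0.80 = 96 patients a year (Section 13), about 8 a month, enrolment may continue while outcomes mature, so 3.6 to 4.9 are upper limits.

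**A symmetric boundary is a recognised choice.** True, but here an asymmetric guideline costs almost nothing.

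**Conclusion.** The concern holds as a gap in the written rule. On either reading of the boundary, the only stated criterion would usually miss even a doubling of leaks, so correcting the percent sign alone would not cure it. The result rests on about 44 evaluable patients per arm, the plan's 20% placebo rate and an assumed secretin rate. It is not sensitive to the choice of test or to modest imbalance. For very large harm (60% v 20%) the 0.005 reading performs adequately, at 83%. The documents do not show that secretin causes leaks or that the DSMB is powerless. The change is worth making because it is cheap and bears on patient safety, although the saving in leaks is modest.

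**What to change.** Split the Section 8 rule by direction.

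- **Benefit:** keep a strict boundary and print it unambiguously, as either 0.005 or 0.005%.
- **Harm:** at the same 88-patient look, whether or not the 66% screen is met, the DSMB considers pausing enrolment if the one-sided Fisher exact p for more leaks on secretin is 0.05 or less (18 secretin leaks if placebo has 9). State that this is non-binding and that the DSMB may set another level in advance.

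Optionally, say that the DSMB also sees the 30-day events of Section 4 by arm at this look.

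The cost is about one sentence. Leaks must already be counted by arm for the 66% screen, so no new data, visit or look is needed. The chance of an unneeded DSMB review is about 3% if leaks are 20% in both arms, and about 0.001% under the planned benefit. A harm-only guideline cannot inflate type I error for benefit.
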